hyperglycemia has a deleterious vascular effect. However, these indices do not directly measure macrovascular flow or microvascular perfusion, vital issues for the tissues per se. A very few human studies have assessed hyperglycemia's effects on microvascular perfusion. In the eye acute hyperglycemia increased retinal flow (measured by videomicroscopy) (12, 13). By contrast, in skin hyperglycemia decreased flow (measured by laser-Doppler flowmetry) (Cuypers, 2000 #6750). Brain perfusion has been measured by arterial spin-labeling MRI in rats (but not in humans) and declined with overnight hyperglycemia with suppressed insulin (27). None of these studies addressed the interaction between insulin or insulin resistance and perfusion and none involved skeletal or heart muscle. CEU provides a noninvasive method to measure two components of microvascular perfusion i.e. microvascular blood volume (MBV) and microvascular flow velocity (MFV). The product of these variables is a measure of microvascular perfusion (28). Our laboratory has extensive experience using CEU to measure perfusion in human cardiac and skeletal muscle. We have previously reported that insulin, exercise, GLP-1, mixed meal ingestion, and angiotensin II each enhance skeletal muscle microvascular perfusion by recruiting under perfused capillaries and increasing MBV (15, 16, and 29). We have also shown that insulin's effect to recruit skeletal muscle microvasculature is lost in insulin resistant subjects with metabolic syndrome, obesity, or when otherwise healthy subjects are rendered insulin resistant by lipid infusion. We have also shown that in healthy volunteers insulin and GLP-1 can each increase MBV in human myocardium. Raising plasma free fatty acid concentrations blunts the effect of insulin on the myocardium as well as on skeletal muscle (25, 29). In these studies of either skeletal or cardiac muscle, MFV was not significantly changed. In a similar vein, an early study using CEU reported that meal ingestion in individuals with type 2 diabetes decreased MBV without affecting MFV (30). As noted earlier, meal ingestion is a more complex stimulus than hyperglycemia per se. A recent CEU study used the pancreatic clamp to provoke hypoinsulinemic hyperglycemia (~220 mg/dl) and reported a decreased myocardial blood flow reserve (provoked by an adenosine agonist) in healthy volunteers (31). No measure was obtained of the direct effect of hyperglycemia. Interestingly, the inhibitory effect of hyperglycemia was attributed to changes in MFV without any significant effect on MBV. The study did not test whether the octreotide (used in the pancreatic clamp) per se affected microvascular responses. Given the scant available data regarding the effect of hyperglycemia on microvascular perfusion in either skeletal or cardiac muscle we propose to establish the vascular impact of acute hyperglycemia in the clinical setting in normal healthy controls.

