	Sponsor
	UVa Statistician. Insert name Answer/Response:
	UVa Investigational Drug Service (IDS)
	X Other: Specify Answer/Response:
	Randomization table obtained from online source-copy included

2. What are the statistical considerations for the protocol?

By design, each of the above protocols affords a paired comparison of the changes which occur between measurements obtained at baseline and at the end of the infusion protocol. Principal endpoints are the changes in microvascular perfusion in both skeletal and cardiac. Referring to Fig 1 for protocol A this comparison will indicate whether 3 ½ hours of octreotide infusion with basal insulin replacement and maintenance of euglycemia per se influences microvascular perfusion in either tissue. As noted above, if octreotide has no specific effect on the primary microvascular endpoint (MBV) then in protocols B, C, and D, we believe paired comparison of baseline and end of study variables will be justified.

This may prove advantageous as it may minimize the effect of day-to-day or week to week variations in responses resulting from uncontrolled variables (diet, exercise, emotional stress etc.) For protocol B this comparison will address whether hyperglycemia for 3 ½ hours in the setting of octreotide infusion, and basal insulin replacement affects microvascular perfusion. Combined protocols A and B analyzed using a 2-way ANOVA will allow analysis of whether time or treatment differences exist and will delineate the effect of hyperglycemia per se on skeletal and cardiac muscle microvascular perfusion, independent of any effect of octreotide per se. In protocols C and D introduce hyperinsulinemia as additional variable under either hyperglycemic or euglycemic conditions with octreotide infusion persisting throughout. Comparing the baseline measurements (C-1) to those obtained at the end of the study (C-2) addresses whether insulin affects microvascular perfusion in the setting of hyperglycemia. Comparison of the

Version Date: November 16, 2017

Page Number: 5 of 34

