- Near infrared spectroscopy (NIRS) This is used to look at hemoglobin content (both oxygenated and deoxygenated) and oxygen saturation in the muscle. A small square fiber optic sensor (2 x 4 inches) will be placed on the skin over the forearm muscle. Light is emitted and as it travels through the different tissue in the arm (bone, fat, muscle, blood etc) it will create a mathematical measurement that has to do with density on the attached computer. The measurement takes 3-5 min.

A. Saline + Octreotide + Euglycemia (~10 hours)

On the day of admission, the subject will be admitted to the CRU at ~ 7:00AM. The subjects will have been asked to fast after 10PM the evening before. Female subjects will have a urine pregnancy test. We will insert 2 peripheral IV lines. One will be in an antecubital vein and this will be used for infusion of saline, octreotide, insulin, glucose and microbubbles. The second will be placed in the lower forearm of the same arm and will be used for sampling. This will be kept patent with a normal saline infusion.

After resting for 1 hour we will begin the study as follows.

- ➤ Blood pressure, heart rate and oxygen saturation will be obtained. If the oxygen saturation <90% the subject will be excluded.
- ➤ Blood will be drawn (~10 cc) for samples of glucose, insulin, and inflammatory cytokines from the sampling IV.
- ➤ We will begin a saline infusion at 30ml/hr.
- > This is considered time -90 min.

We will measure insulin every 30 minutes for duration of study (~18cc).

Between -30 and 0 minutes

- > We will measure NIRS of forearm muscle
- > Next we will measure PWV followed by AI
- Next we will measure FMD
- Next we will perform CEU of the heart and skeletal muscle
- > Subjects will be placed on a continuous cardiac monitor for 30 minutes following the end of the microbubble infusion. There will always be a resuscitation cart as well as qualified personnel available should the need arise.

Version Date: November 16, 2017

Page Number: 9 of 34

- ➤ We will repeat the blood sampling (~10cc) performed at time -90.
- We will begin an infusion of Octreotide (30ng/kg/min).
- ➤ We will begin an insulin infusion (dose is 0.15mU/kg body wt/min).
- We will also begin glucose infusion (20% variable rate) to maintain euglycemia.
- > This is considered time 0 min.
- ➤ We will measure plasma blood glucose every 10 min through 240 min (~23cc blood).

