- ➤ The values for blood glucose are measured immediately and used to adjust the rate of infusion of a glucose solution (20% dextrose) in order to maintain plasma glucose within 10% of the fasting concentration.
- We will repeat the entire sequence of vascular measurements between 210 and 240 minutes.
- ➤ We will also repeat blood draw for glucose, insulin and inflammatory cytokines (~10cc).
- ➤ At time 240 minutes the study is complete and the insulin and octreotide infusion will be stopped.
- Subject will be fed a meal.
- ➢ Blood glucose measurements will continue to be made at 10 minute intervals (~15 cc of blood) and the rate of the glucose infusion adjusted to maintain normal blood glucose levels. This will continue until blood glucose is within normal range without the need for the glucose infusion.
- ➤ We will also continue to test blood glucose every 15 minutes (~5cc blood) for one hour after glucose infusion stopped to be sure that blood glucose levels stay within normal range.

When the sampling for blood glucose is complete subjects will have all catheters removed and vital signs done. If stable they will be discharged.

Total blood taken for this admission is approximately ~91cc.

B. Octreotide + Hyperglycemia admission (~10hrs)

On the day of admission, the subject will be admitted to the CRU at ~ 7:00AM. The subjects will have been asked to fast after 10PM the evening before. Female subjects will have a urine pregnancy test. We will insert 2 peripheral IV lines. One will be in an antecubital vein and this will be used for infusion of octreotide, insulin, glucose and microbubbles. The second will be placed in the lower forearm of the same arm and will be used for sampling. This will be kept patent with a normal saline infusion.

After resting for 1 hour we will begin the study as follows.

- ➤ Blood pressure, heart rate and oxygen saturation will be obtained. If the oxygen saturation <90% the subject will be excluded.
- ➤ Blood will be drawn (~10cc) for samples of glucose, insulin, and inflammatory cytokines from the sampling IV.
- We will begin an infusion of Octreotide (30ng/kg/min).

Version Date: November 16, 2017

Page Number: 10 of 34

- We will also begin the insulin infusion (dose is 0.15mU/kg body wt/min).
- We will also begin glucose infusion (20% at variable rate) to maintain euglycemia.
- > This is considered time -90 min.
- ➤ We will draw blood every 10 min to measure blood glucose from time -90 min to 0 min (~12cc).

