- ➤ The values for blood glucose are measured immediately and used to adjust the rate of infusion of a glucose solution (20% dextrose) in order to maintain plasma glucose within 10% of the fasting concentration

We will measure insulin every 30 minutes for duration of study (~18cc).

At time 0 minutes

- ➤ We will measure NIRS of forearm muscle
- Next we will measure PWV followed by AI
- Next we will measure FMD
- Next we will perform CEU of the heart and skeletal muscle
- > Subjects will be placed on a continuous cardiac monitor for 30 minutes following the end of the microbubble infusion. There will always be a resuscitation cart as well as qualified personnel available should the need arise.
- ➤ We will repeat the blood sampling (~10cc) performed at time -90.
- Next we will adjust the glucose rate to achieve hyperglycemia (200mg/dl).
- We will measure plasma blood glucose every 5 minutes starting at time 0 min through 240 min (45cc blood).
- > The values for blood glucose are measured immediately and used to adjust the rate of infusion of a glucose solution (20% dextrose) in order to raise and maintain plasma glucose concentration at 200mg/dl.
- > We will repeat the entire sequence of vascular measurements between 210 and 240 minutes.
- ➤ We will also repeat blood draw for glucose, insulin and inflammatory cytokines (~10cc).
- > At time 240 minutes the octreotide, insulin and glucose infusion will be stopped.
- > Subject will be fed a meal.
- ➤ Blood glucose measurements will continue to be made at 10 min intervals (~ 15 cc of blood) until blood glucose is within normal range. We will continue to test blood glucose every 15 minutes (~5cc blood) for one hour to be sure that blood glucose levels stay within normal range.

When the sampling for blood glucose is complete subjects will have all catheters removed and vital signs done. If stable they will be discharged.

Total blood taken for this admission is approximately ~125cc.

Version Date: November 16, 2017

Page Number: 11 of 34

C. Octreotide + Hyperglycemia + insulin clamp (~10 hours)

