7. Will drug need to be prepared by the UVa Investigational Drug Service (IDS)?x YES (Octreotide) D20 dispensedx NO- Drug will be prepared and/or administered per package insert The insulin will be mixed in normal saline and 2 ml of subjects own blood on study day.
▶ IF YES, complete the following information under 7a-7d. If you need assistance completing this section contact the Investigational Pharmacists at [name]
7a. Concentration Standard X Non- Standard-Specify Answer/Response: Octreotide- The dose is 30ng/kg/min-4 admits are 5 hr infusions and Admit A is 3.5-see fig 1
7b. Diluents

Version Date: November 16, 2017 Page Number: 21 of 34

Standard Non- Standard-Specify Answer/Response: Octreotide to be mixed with normal saline.
7c. Stability after preparedx Standard Non- Standard-Specify Answer/Response
7d. Special storage requirementsx Standard Non- Standard-Specify Answer/Response:
8. Are there any special handling instructions mandated by the study (e.g. weighing hazardous materials)? Answer/Response: No
► IF YES, provide specifics Answer/Response:
9. Does the protocol provide provisions for dose titration, dose reductions, and or rechallenged (if drug is stopped), etc.? Answer/Response: No
► IF YES, provide specifics Answer/Response:
10. How will missed doses be handled? Answer/Response: N/A
11. Will a comparator (active or placebo) be utilized in the protocol? Answer/Response: No
► IF YES, comparator is: Active FDA approved drug: Provide name and dose of drug: Answer/Response
Placebo: Describe: Answer/Response:
12. Does this study involve research on a drug, biologic, supplement or food additive? Answer/Response: Yes
► IF YES, is this study investigator initiated? Answer/Response: Yes

Version Date: November 16, 2017 Page Number: 22 of 34

IF YES, answer questions # 13 and 14
IF NO, answer question # 13 only.

13 Are you using a drug/supplement/ food additive in a manner not approved by the FDA?

Answer/Response: Yes

Insulin for euglycemia clamp is used to look at insulin sensitivity. This drug has been used in this manner for 60+ years.

Definity is used in the same manner for both heart (FDA approved) and skeletal muscle, we are just moving the probe to the arm after looking at the heart

Octreotide has been approved for patient use since 1988. We are using it to decrease endogenous insulin, glucagon and GH secretion during clamp.

IF YES, answer questions 13a-13f

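### The A-versus-B ANOVA cannot separate hyperglycemia from octreotide, because A's baseline precedes octreotide and B's comes about 90 minutes into it

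*Combined protocol and SAP*

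**What the plan says.** Statistical Considerations, item 2, plans a 2-way ANOVA (time by treatment) on admissions A and B and states that it "will delineate the effect of hyperglycemia per se on skeletal and cardiac muscle microvascular perfusion, independent of any effect of octreotide per se". No condition is attached to that statement. The same item does contain a condition, "if octreotide has no specific effect on the primary microvascular endpoint (MBV) then in protocols B, C, and D, we believe paired comparison", but it governs only the baseline-to-end tests within B, C and D.

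The timings are in the procedure lists under Biomedical Research, item 1:

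- **Admission A.** Only saline runs from −90 min. The vascular baseline is taken "Between -30 and 0 minutes". Octreotide, basal insulin and glucose start after it, at the point labelled "This is considered time 0 min".
- **Admission B.** Octreotide starts at −90 min, and with it basal insulin ("We will also begin the insulin infusion (dose is 0.15mU/kg body wt/min") and glucose. The vascular baseline is at time 0, and only then does the glucose target change: "Next we will adjust the glucose rate to achieve hyperglycemia (200mg/dl".
- **Both.** End measurements are at 210–240 min.

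Pharmacy item 7a also gives A the shorter octreotide infusion: "admits are 5 hr infusions and Admit A is 3.5".

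**The concern.** A control admission removes the effect of a background infusion only if that infusion contributes equally to the change in both admissions. Here A's change runs from no octreotide to octreotide, while B's runs from octreotide to octreotide plus hyperglycemia. Subtracting one from the other can put the octreotide effect into the contrast instead of removing it.

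This ANOVA is the only between-admission test the plan names for hyperglycemia alone on microvascular perfusion, which is hypothesis (a). If octreotide or basal insulin alters perfusion early, the interaction can show a hyperglycemia effect that does not exist or hide one that does. The authors treat octreotide's own effect as an open question. Of an earlier pancreatic-clamp study, the Background says: "The study did not test whether the octreotide (used in the pancreatic clamp) per se affected microvascular responses".

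**Working it through.** **Minutes on octreotide at each measurement, from the procedure lists**

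| Measurement | Minutes on octreotide | Glycemia |
|---|---|---|
| A1 | 0 | normal |
| A2 | 210–240 | normal |
| B1 | about 90 | normal |
| B2 | 300–330 | high |
| C1 | 180–210 | high for 90–120 min |
| D1 | 180–210 | normal |

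The lists imply 4 h of octreotide in A and 5.5 h in B; Pharmacy item 7a gives 3.5 h and 5 h, and counts four other admissions where there are three. Those passages must be reconciled. The 1.5 h gap between A and B is the same in both.

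**The contrast.** Let O(t) be the effect of t minutes of octreotide with basal insulin, and H the hyperglycemia effect.

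(B2 − B1) − (A2 − A1) = H + [O(300) − O(90)] − [O(210) − O(0)]

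If O is complete by 90 min and then stable, this is H + 0 − O = H − O. The time main effect is the mean of the two changes, (H + O)/2. The treatment main effect is [O + (O + H)]/2 − [0 + O]/2 = (H + O)/2. None of the three isolates H. The interaction is unbiased when O(90) − O(0) = O(300) − O(210). Examples are no effect, growth linear in time, or an effect absent at 90 min and complete by 210 min.

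**Bias as a percentage of O(300), for assumed time courses**

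| Time course | Interaction | B2 − A2 | B2 − B1 | C1 − D1 |
|---|---|---|---|---|
| Complete by 90 min | −100 | 0 | 0 | 0 |
| Half-time 30 min | −87 | 1 | 12 | 0 |
| Half-time 60 min | −61 | 6 | 33 | 0 |
| Half-time 120 min | −35 | 15 | 51 | 0 |
| Linear | 0 | 30 | 70 | 0 |

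The half-time rows use O(t) = 1 − 2^(−t/h). For h = 60: O(90) = 0.646, O(210) = 0.912 and O(300) = 0.969. The bias is (0.969 − 0.646) − 0.912 = −0.589, and −0.589/0.969 = −61%.

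**An SD to work with.** The documents give none, so the stated sample size of 22 cannot be reproduced. Item 2 says 12–14 subjects suffice to detect a 30% difference. If that meant 80% power at two-sided 0.05, the SD of change would be 33.8–37.0%. The same power at exactly 16 or 20 subjects would imply 40.0% or 45.4%. I take 35%, with a range of 25–45%. The correlation ρ between the two changes is set at 0 to 0.5.

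**Rejection rates.** Noncentral t, two-sided 0.05, SD of the contrast = SD × √(2(1 − ρ)). That is 49.5% at ρ = 0 and 35% at ρ = 0.5. True H = 0, O complete by 90 min:

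| O | n = 22 | n = 16 |
|---|---|---|
| 5% | 7–10% | 7–8% |
| 10% | 15–25% | 12–19% |
| 15% | 27–48% | 21–36% |
| 30% | 77–97% | 62–89% |

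At O = 15% and n = 22 the range is 48–77% for SD 25% and 18–32% for SD 45%. With a 60-minute half-time and O = 15%, the rate at SD 35% and n = 22 is 13–22%.

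**Masking.** With H = −30% and O = −15%, complete by 90 min, the contrast is −30 + 15 = −15%. Power at n = 22 falls from 77–97% to 27–48%.

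**Can A's own test settle whether octreotide acts?** At SD 35%, A's baseline-to-end test has 25% power (n = 22) or 19% power (n = 16) to detect a 10% octreotide effect. A non-significant result would say little.

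**The case against.** The strongest reply is that the harm is conditional. If octreotide with basal insulin does nothing to perfusion, the contrast is unbiased, and no document supplies an effect size, time course or SD. The 77–97% row needs an octreotide effect as large as the 30% target. That stands, and the rates are illustrations only. It does not rescue the wording, which claims independence of any octreotide effect.

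Second, the B2 − B1 test is also planned. It is free of a stable octreotide effect, so when the interaction is at its worst it would disagree with a false signal. This mitigates the problem without removing it: B2 − B1 is exposed to time drift and slow onset, and the plan allows it only if octreotide has no effect.

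Third, the same four cells yield B2 − A2 as a simple effect, and the plan does not say which ANOVA term decides. That is fair. The contrast is unspecified, and the claim fails for all three standard terms.

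Fourth, the timing is uncertain. The figure is not shown, and B's baseline sequence, listed at time 0, takes time to perform. Placing B1 at 120 min makes the interaction bias larger (from −61% to about −71.5% at a 60-minute half-time), and linear growth then gives −10% instead of zero.

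Finally, between-admission contrasts lose the within-day precision that item 2 values. That is a genuine cost.

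**Conclusion.** The concern holds. The mismatch in octreotide, basal insulin and glucose exposure at baseline is plain from the procedure lists, and the pharmacy section's durations agree with it. The independence claimed for the A/B ANOVA is not a property of this design. Confidence is high on the mismatch and the algebra.

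The size and direction of the bias are unknown. They depend on an octreotide effect and time course that the documents do not give, and the rejection rates rest on the assumed SD and correlation. An effect near zero would do little harm. An early effect of 10–15% would raise false positives to several times the nominal 5%, or remove about half or more of the power when it has the same sign as H. The planned comparison of changes between C and D is unaffected, because those admissions share the same octreotide timing. This should be fixed before analysis.

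**What to change.** Change the analysis text; no infusion, visit or measurement need change.

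1. Delete the clause claiming that the A/B ANOVA is independent of octreotide.
2. For the 3½-hour question, prespecify B2 versus A2 within subject. State that it assumes a stable octreotide effect between about 210 and 300 minutes of exposure.
3. For hypothesis (a), which speaks of inhibition within 3 hours, prespecify C1 versus D1. These match on octreotide time, basal insulin and clock time and differ by design in glycemia. State that this contrast covers only 90–120 minutes of hyperglycemia.
4. Say which of the two is primary. They are different estimands, so the choice belongs to the investigators.
5. Keep B2 − B1 as supporting, noting that it is not protected against time drift.
6. Report A's change with its confidence interval, and do not use its non-significance to license other tests.
7. Show A1, B1, D1 and A2 (0, 90, 180–210 and 210–240 minutes of octreotide, all euglycemic) descriptively, as a partial check on the time course. The plan already compares D1 with A2.

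The cost is day-to-day variance. With day-to-day SD d and measurement SD e, var(B2 − A2) = 2d² + 2e² and var(interaction) = 4e², so B2 − A2 is less precise only if d exceeds e. At an SD of change of 35%, e = 35/√2 = 24.7 points if changes are uncorrelated. If a correlation of 0.5 reflects shared subject response, 4e² = 35² and the threshold is 17.5 points. Both contrasts are less precise than a pre/post test, whose variance is 2e².

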12. Will your study involve measures (C-SSRS/BID/SCID etc.) used to assess for depression and/or suicidality for research purposes? No

Answer this question YES if any of the following apply:

13. Where will the study procedures be done?

Check One:

UVA medical center facilities (In patient or outpatient)
___x_ UVa, but not medical center facilities: LIST specific location Answer/Response:
Clinical Research Unit (CRU)

____ Other LIST specific location Answer/Response:

Version Date: November 16, 2017

Page Number: 17 of 34

14. If the study in	nvolves medical risk and study procedures will be done outside of the UVa
Medical Center v	what is your plan to protect the subjects in case of a medical emergency?
Check all app	licable options:
X	MD, RN, onsite during procedures
	Individual trained in CPR on site during procedures
	AED and Individual trained to use it onsite
	Call 911
	Other: Describe Answer/Response:

Unapproved Device Use

(Unapproved Device being used but not evaluated)

INSTRUCTIONS: This section is to provide the IRB with information about the safety of a device that is being USED, but not evaluated in this study for safety and efficacy. The device may have FDA approval and is being used for a non-approved indication OR the device may not have FDA approval [these are typically known as Research Use Only (RUO) Devices]. Again the RUO Device is only being USED and NOT being evaluated for safety and efficacy in this study. The information below will be used by the IRB to make a minimal risk determination regarding this protocol.

1. List name of device(s) being used in an unapproved manner in this protocol.

Per the statute: Federal Food, Drug, and Cosmetic Act Sec 201.h [21USC321] DEVICE: (h) The term "device" (except when used in paragraph (n) of this section and in sections 301(i), 403(f), 502(c), and 602(c)) means an instrument, apparatus, implement, machine, contrivance, implant, in vitro reagent, or other similar or related article, including any component, part, or accessory, which is—

- (1) recognized in the official National Formulary, or the United States Pharmacopeia, or any supplement to them,
- (2) intended for use in the diagnosis of disease or other conditions, or in the cure, mitigation, treatment, or prevention of disease, in man or other animals, or
- (3) intended to affect the structure or any function of the body of man or other animals, and which does not achieve its primary intended purposes through chemical action within or on the body of man or other animals and which is not dependent upon being metabolized for the achievement of its primary intended purposes.

Answer/Response:
Harvard infusion pump
Oxiplex TS (near infrared spectroscopy)

2. Do you confirm the device is only being USED and NOT being evaluated in this study?

Version Date: November 16, 2017

Page Number: 18 of 34

Answer/Response: Yes

3. Is the device a Research Use Only (RUO) device?

IF YES, submit the manufactures brochure/information regarding the RUO with other documents at the time of pre-review.

IMPORTANT: The RUO designation is made by the FDA.

The package insert MUST stipulate that this is a RUO device.

Answer/Response:

Only the Oxiplex TS-FDA confirmation on file

▶ If the device is a RUO device, do you agree to use the device according to instructions in the manufacturers brochure?

Answer/Response: Yes

► If the device is NOT a RUO device, is the device currently approved for any indication?

Answer/Response:

No for Harvard pump

► If the device is currently approved list the indication:

INSTRUCTIONS: Also submit the Manufacturer's Brochure

Answer/Response:

▶ If the device is currently approved, do you confirm that results will not be used in clinical care of the subject (e.g. will not be used for diagnosis or treatment?)

Answer/Response:

4. In how many humans has this device been used previously as it is being used in this study?

Answer/Response:

Harvard Pump: We have used this device in this manner for 24 years at UVA and have done

2000+ studies

Oxiplex TS-unknown

5. Describe pertinent human data that is available regarding the safety of this device as you are using it in this protocol.

Answer/Response:

Harvard pump-N/A

Oxiplex TS-unknown

6. If this protocol will be used in children, describe any previous use of this device with children of a similar age range as it is being used in this study.

Answer/Response: N/A

Version Date: November 16, 2017

Page Number: 19 of 34

7. What steps will be taken to minimize risk?

Answer/Response: Qualified personnel will always be at the beside when either of these devices are used

8. Would you consider the use of this device to be minimal risk? Why or why not?

Minimal Risk: probability and magnitude of harm or discomfort anticipated in the research are not greater in and of themselves than those ordinarily encountered in daily life or during the performance of routine physical or psychological examinations or tests. 45CFR46.102

Answer/Response:

Harvard pump--Minimal risk as this is just used for relatively short infusions and study team present and monitoring at all times.

Oxiplex TS-Minimal risks as non-invasive measurement that takes a few minutes.

Drug Information

1 What is the drug name, manufacturer and IND# if available?

Answer/Response:

Drug name	Drug Source	IND#
Octreotide	Novartis	N/A
Insulin	Novo Nordisk	N/A
Definity	Lantheus	N/A
Microbubbles	Medical Imaging	
Dextrose 20%	Hospira	N/A

2. If IND application has been submitted to the FDA, who is the Principal Investigator on the IND?

Answer/Response: N/A

3. What is the phase or stage of this study?

e.g. Phase 1,2 or 3, pivotal, pilot, post-marketing

Answer/Response: N/A

Pharmacy-Investigational Drugs/Biologics

1. What is the name of the investigational drug/biologic?

Answer/Response:

Regular insulin

Octreotide

Definity

Dextrose 20%

Version Date: November 16, 2017

Page Number: 20 of 34

2. Where will the subjects be seen for the administration/dispensing of the drug? Inpatient Unit: Specify Answer/Response:
X Outpatient Unit: Specify Answer/Response: Clinical Research Unit
3. What dose will be utilized in this study? Answer/Response: Regular insulin-1mU/kg/minute IV on clamp days otherwise low rate of 0.15mU/kg/min). Definity-1 vial per study day Octreotide – 30ng/kg/min
4. What will be the frequency of dosing in this study? Answer/Response: Regular insulin-varying times (depending on study) low dose same schedule as Octreotide except during insulin clamp which is a higher dose. Please see protocol figure provided. Definity-1 vial per study day Octreotide — varying times depending on study- please see protocol figure 1 provided. Dextrose 20%-entire 5 hrs (at variable rate) for each admit except visit A-see figure 1. 5. What will be the duration of dosing in this study? Answer/Response: As noted above 6. What route of administration will be utilized? Answer/Response: Regular insulin-IV Definity-IV Octreotide-IV Dextrose 20 %- IV
7. Will drug need to be prepared by the UVa Investigational Drug Service (IDS)?x YES (Octreotide) D20 dispensedx NO- Drug will be prepared and/or administered per package insert The insulin will be mixed in normal saline and 2 ml of subjects own blood on study day.
▶ IF YES, complete the following information under 7a-7d. If you need assistance completing this section contact the Investigational Pharmacists at [name]
7a. Concentration Standard X Non- Standard-Specify Answer/Response: Octreotide- The dose is 30ng/kg/min-4 admits are 5 hr infusions and Admit A is 3.5-see fig 1
7b. Diluents

Version Date: November 16, 2017 Page Number: 21 of 34

Standard Non- Standard-Specify Answer/Response: Octreotide to be mixed with normal saline.
7c. Stability after preparedx Standard Non- Standard-Specify Answer/Response
7d. Special storage requirementsx Standard Non- Standard-Specify Answer/Response:
8. Are there any special handling instructions mandated by the study (e.g. weighing hazardous materials)? Answer/Response: No
► IF YES, provide specifics Answer/Response:
9. Does the protocol provide provisions for dose titration, dose reductions, and or rechallenged (if drug is stopped), etc.? Answer/Response: No
► IF YES, provide specifics Answer/Response:
10. How will missed doses be handled? Answer/Response: N/A
11. Will a comparator (active or placebo) be utilized in the protocol? Answer/Response: No
► IF YES, comparator is: Active FDA approved drug: Provide name and dose of drug: Answer/Response
Placebo: Describe: Answer/Response:
12. Does this study involve research on a drug, biologic, supplement or food additive? Answer/Response: Yes
► IF YES, is this study investigator initiated? Answer/Response: Yes

Version Date: November 16, 2017 Page Number: 22 of 34

IF YES, answer questions # 13 and 14
IF NO, answer question # 13 only.

13 Are you using a drug/supplement/ food additive in a manner not approved by the FDA?

Answer/Response: Yes

Insulin for euglycemia clamp is used to look at insulin sensitivity. This drug has been used in this manner for 60+ years.

Definity is used in the same manner for both heart (FDA approved) and skeletal muscle, we are just moving the probe to the arm after looking at the heart

Octreotide has been approved for patient use since 1988. We are using it to decrease endogenous insulin, glucagon and GH secretion during clamp.

IF YES, answer questions 13a-13f

You may reference the non-IRB protocol to answer these questions.

13a. Describe pertinent animal data that is available regarding the toxicity/safety of this drug.

Answer/Response: Please see attached package insert for all drugs

13b. Describe pertinent human data that is available regarding the toxicity/safety of this drug.

Answer/Response: Please see attached package insert for all drugs

13c. Have there been any human deaths associated with this drug?

Answer/Response: Please see attached package insert for all drugs

13d. In how many humans has this drug been used previously?

Answer/Response: Please see attached package insert for all drugs

13e. If this protocol will be used in children describe any previous use of this drug with children of a similar age range.

Answer/Response: N/A

14. Do the following criteria apply? NO Check all that apply

The investigation is intended to be reported to FDA as a well-controlled study	in
support of a new indication for use or intended to be used to support any other	
significant change in the labeling for the drug;	

If the drug that is undergoing investigation is lawfully marketed as a prescription drug product, the investigation is intended to support a significant change in the advertising for the product;

Version Date: November 16, 2017

Page Number: 23 of 34

The investigation does involve a route of administration or dosage level or use in a patient population or other factor that significantly increases the risks (or decreases the acceptability of the risks) associated with the use of the drug product.
If Not checked- explain why you believe the risk to subjects is not increased:
Answer/Response:
[name] has extensive research experience administering insulin to look at insulin sensitivity in the normal and diabetic population. Insulin has been safely used in this manner for over 60 years. Procedures are in place to minimize the risk to subjects such as q 5 min blood glucose monitoring during the insulin clamp procedure. Although the Definity is approved for imaging cardiac instead of skeletal muscle, we are using the same dose and route of administration. We are imaging cardiac and skeletal muscle in this study.
Octreotide has been approved for patient use for a variety of reasons since 1988. We are using it to decrease endogenous insulin secretion during the insulin clamp. It has also been used in this way for research for many years.
X The investigation will be conducted in compliance with the requirements for institutional review set part in part 21CFR56 and with the requirements for informed consent set forth in part 21CFR50; and
X The investigation will be conducted in compliance with the requirements of 21CFR312.7 (Promotion and charging for investigational drugs)

15. Is this a post-marketing study?

This item must be checked.

Answer/Response: No

► IF YES is the study required to be done by the FDA?

Answer/Response: No

Version Date: November 16, 2017

Page Number: 24 of 34

Subject Compliance with Study Procedures

1. Explain how the study team will monitor the subject for compliance with the study procedures.

(e.g. study team will administer study drug/ study interventions, study drug inventory of dispensed and returned drug, diary etc.)

Answer/Response:

There is nothing in between visits to monitor. Everything is done/infused on the study days.

2. Describe criteria for when a subject is considered to be non-compliant with study procedures.

(e.g. subject returns more than 20% of the study drug, subject misses 20% of study visits)

Answer/Response: N/A

Specimens

Specimen Information

1. Describe the type of specimen to be used:

Answer/Response:

Urine and Blood

2. Will the specimen be obtained BEFORE a subject has signed a consent form?

Answer/Response: No

3. Will you be using discarded specimens?

Answer/Response: No

▶ IF YES, do you confirm that it will be obtained either from pathology, a clinical lab or the UVA Biorepository & Tissue Research Facility (BTRF)?

Answer/Response:

▶ IF you will not obtain the specimen from the sources listed above, describe the process for obtaining the discarded tissue.

Answer/Response:

Answer the following questions as it pertains to ALL blood being drawn for this study.

► IF NO, where will blood be drawn? Check all that apply _____in clinical labs

______in chinical labs
______X ____ in the clinical research unit (CRU)
______ in a clinical setting
______ in a research lab which has an IBC#
Other: Explain Answer/Response:

Version Date: November 16, 2017

Page Number: 25 of 34

▶ IF NO, who will draw the blood?
a member of the study team who is an individual licensed to practice
medicine or osteopathy, a nurse practitioner, or a physician assistant employed by UVa School of Medicine
